6.2 Other treatment(s)

6.2.1 Rescue medication

Management of severe malaria consists of an IV antimalarial (cipargamin or artesunate in the study) followed by a full course of oral standard of care (Coartem in this study). Hence, rescue medication use will also be either IV medication or oral medication as applicable.

Participants randomized to IV artesunate will not be administered any other IV antimalarial as rescue medication since IV artesunate is the only standard of care. Participants randomized to IV cipargamin may be rescued with IV artesunate, if they meet the following pre-defined criteria:

- Parasite clearance < 90% at 24 hours post treatment initiation
- Clinical decline of severe malaria symptoms (per Investigator) at any time
- Participants not able to take oral antimalarial along with presence of parasites at 72 hour post treatment initiation
- Participants developing signs or symptoms of severe malaria after shift to oral standard of care (Coartem) until end of the study (Day 29).

In addition, participants developing safety concerns due to cipargamin (Refer also [Section 16.1](#), [Section 16.2](#)) can be rescued with IV artesunate.

After completion of full course of Coartem, participants meeting the following criteria will be administered another ACT (as per local guidance) as an oral rescue medication:

- Parasitemia at any time with or without temperature > 37.5°C

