dosing. To limit the total exposure of IV cipargamin in this first study of IV cipargamin in malaria patients, participants will receive a maximum of 3 daily doses. For severe cases, the total duration of IV therapy (either IV cipargamin followed by IV artesunate or IV artesunate alone) will be defined by the medical condition of the participants and the prescribing information of IV artesunate.

Cohorts 1-2

The lowest dose selected for Cohorts 1-2 i.e. 20 mg is expected to CCI [REDACTED] 1 [REDACTED]. As such, this dose is expected to provide equivalent or faster initial parasite clearance than the standard of care i.e. artesunate and thereby minimize the risk for severely ill participants due to slow parasite clearance.

A dose of 40 mg is expected to provide CCI [REDACTED] observed with oral cipargamin in participants with uncomplicated malaria (refer Figure 4-1 below). Hence, a fast parasite clearance rate is expected to be achieved in all the participants and a full dose response curve can be obtained to ensure that the appropriate benefit risk relationship is established in adolescent and adult participants before dosing children below 12 years in Cohorts 3-5. The anticipated exposure with 40 mg dose is comparable to the highest exposure, which was achieved in oral cipargamin in study CKAE609A2202 without any safety issues.

In conclusion, the inclusion of 20 and 40 mg doses in Cohorts 1-2 will cover a wider exposure range and facilitate the selection of an appropriate dose for later Cohorts 3-5.

Cohorts 3-5

A single dose level with the best benefit risk potential will be evaluated in participants < 12 years old based on interim assessment of data from Cohorts 1 and 2. The population PK and / or PBPK model will be developed / up-dated with this data to predict exposures in participants from Cohort 3-5. If required, the speed of IV bolus administration may be adjusted to keep the Cmax within the safe range as determined in Cohorts 1-2. CCI [REDACTED]

[REDACTED]

Figure 4-1

CCI

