6.1.2 Additional study treatments

6.1.2.1 Oral medication (standard of care)

All sites will receive Coartem as standard of care for oral treatment as per local practice. Following criteria are recommended for specified timepoints when switching participant from IV therapy to oral therapy as mentioned in below [Table 6-4](#):

First timepoint to switch participant from IV therapy to oral is at 48 hour. However, if a participant is not able to tolerate oral therapy then continue with IV treatments and evaluate again at 72 hour timepoint.

Table 6-4 Criteria for switch to oral medication (standard of care)

Time	Decision criteria	Decision
0 hours	Review screening results	Start dosing with IV therapy
24 hours	Assess rescue medication criteria	Continue IV therapy (and assess rescue medication criteria for participants on IV cipargamin) (see Section 6.2.1)
48 hours (Day 3) (1 st timepoint for a switch to oral therapy)	Assess the feasibility of administering oral medication	Start Coartem, if switch criteria are met as per label. Otherwise continue IV therapy (and assess rescue medication criteria per Section 6.2.1)
72 hours (Day 4) onwards	Assess the feasibility of administering oral medication at every 24 hours	Start Coartem, if switch criteria are met as per label. Otherwise continue IV artesunate or switch to IV artesunate therapy (for participants on IV cipargamin as per Section 6.2.1). Hospitalization should be extended till the time participant has not switched to oral therapy and assessments to be repeated as Day 4 if hospitalization is required beyond Day 4 (see Table 8-1 , Table 8-2)

Intravenous artesunate can be administered to a maximum of 7 days based as per supplied labels. Most participants after switching to oral therapy will be discharged from hospital with full oral course of Coartem for 3 days. Site to instruct participant (or participant's representative) on intake of oral therapy per label.

After switching to oral therapy (Coartem), if there are efficacy or safety concerns, the participant will be administered another ACT ([Section 6.2.1](#)) as per local treatment guidance.

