6.1.4 Treatment duration

Participants will be treated with IV cipargamin (KAE609) once daily for at least 24 hours (2 doses) and a maximum of 48 hours (3 doses). Participants requiring prolonged IV treatment will be switched to IV artesunate and treated according to local practice. Participants in control arms will receive IV artesunate for at least 24 hours (3 doses) and for a maximum of 7 days if necessary as per label or until oral Coartem (standard of care) can be tolerated, whichever is earlier (see criteria for switch to oral therapy in [Section 6.1.2.1](#)).

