¹⁰ ECG's should be taken in triplicate within 5 min after resting for at least 10 min in the supine position. Last ECG should be taken 24 hours after final IV drug dose. Pre-dose ECG can be taken in less than 30 mins before first dosing and all post baseline ECG assessments (from D2 and D2 onwards) should be taken in less than 15 min post-dose.

¹¹ ECG assessment after drug administration.

¹² For all Cipargamin (KAE609) participants only. Rich PK collection with 1 ml blood. For scheduled time: Pre-dose samples (0, 24h, 48h, 72h) should be taken in less than 15 min before the dosing; Post-dose samples as following (Day 1: 2 min: + 1 min; 10 min: ± 2 min; >10 min - 3 h: ± 10 min; >3 - <24 h: ± 30 min; Day 2: 24h02m: + 1 min; >24h10 min - 27 h: ± 10 min; >27 - <48 h: ± 30 min; Day 3: 48h02m: + 1 min; >44h10 min - 52 h: ± 10 min; >52 - <72 h: ± 30 min) Exact time to be recorded for samples taken in follow-up period (Day 6 and Day 8).

¹³ For all Cipargamin (KAE609) participants only

CCI
[REDACTED]

¹⁸ Minimum and maximum duration of IV cipargamin will be 24 H (2 doses) and 48 H (3 doses). If cipargamin participants require IV therapy beyond 3 doses, refer rescue medication criteria ([Section 6.2.1](#)). Minimum and maximum duration of IV artesunate will be 24 H (3 doses) and 7 D (8 doses).

¹⁹ Day 1, 12 h dosing only for participants receiving IV artesunate

²⁰ First timepoint to switch from IV therapy to oral therapy is at 48 H. If participant is eligible, administer Coartem as per label. However, if participant is not able to tolerate oral therapy then continue with IV treatments and evaluate again at D4 and every 24h until participant receives oral therapy.

²¹ All medication administered or taken by the participants up to 72 hours prior first dose has to be reported as prior medication in the appropriate Case Report Forms.

²² EOS = End Of Study (D29) OR PSW = Premature Study Withdrawal (to be performed at last visit of the participant getting discontinued from the study)

Period	Screening	Hospitalization														Discharge day ¹	Follow-up						Unscheduled visit
Visit Name	Screening ²	D1 ²										D2				D3 ³	D4	D6	D8	D15	D22	D29 (EOS/PSW) ⁴	Unscheduled visit
Days	(-3 to 0 h)	1										2				3	4	6	8	15 ±1	22 ±2	29 ±2	-
Time (post-dose)	-	0h ⁵	2m	30m	1h	2h	4h	6h	12h	18h	24h	30h	36h	42h	48h	72h	120h	168h	336h	504h	672h	-	
Inclusion / Exclusion criteria	X																						
Informed consent ⁶	X																						

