2.4.2 Prior, concomitant and post therapies

Prior and concomitant medications will be summarized in separate tables by treatment group.

Concomitant IV rescue and other anti-malarial medications will also be summarized by treatment group and drug.

Note – If a patient is randomized to IV cipargamin regimen but receiving IV artesunate per investigator's discretion, the IV artesunate will be classified as rescue medication. IV artesunate as rescue medications will be captured in DAR CRF whereas, other antimalarials will be recorded in concomitant medications CRFs.

Prior medications are defined as drugs taken and stopped prior to the first dose of study medication. Any medication given at least once between the day of first dose of study medication and the last day of study visit will be a concomitant medication, including those which were started pre-baseline and continued into the treatment period.

Prior and concomitant medications will be coded according to the latest version of WHO Drug Reference List dictionary which employs the ATC. The number and percentage of patients taking prior and concomitant medications will be summarized for each treatment by ATC class and preferred term (PT).

Number and percentages of the patients using concomitant medications in the management of signs and symptoms of severe malaria by treatment group will be summarized. A listing will be provided. These drugs will be identified from the clinical database prior to database lock. Number and percent of patients receiving concomitant non-study drug antimalarial will be provided by treatment group (See [Table 5-11](#)).

A listing of the patients who received prohibited prior and concomitant drugs will be provided. It is anticipated that only few patients will receive prohibited prior and concomitant drugs. Separate summary table for prohibited prior and concomitant drugs may also be provided if a higher number of patients are reported to receive such medicines. Prohibited drugs will be identified from the clinical database prior to database lock.

Safety set will be used. In case of differences in the safety set and FAS, the analysis will also be repeated on FAS.

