2.15.2 Stopping criteria for the study

Data related to participant's efficacy and safety will be continuously monitored by the sponsor. If participants randomized to any IV cipargamin arms meet either the safety criteria or lack of efficacy criteria as listed in [Table 2-14](#) below, the study may be paused and a DMC review conducted.

Table 2-14 Criteria to temporarily pause the recruitment and initiate DMC review

Cohorts with planned recruitment	Number of participants meeting the safety criteria*	Number of participants meeting the lack of efficacy criteria**
Cohort with 6 participants	2	2
Cohort with 14 participants	2	2
Cohort with 20 participants	3	3
Cohort with 38 participants	6	6
Throughout the study (116 participants within a single IV cipargamin treatment arm)	14	14

*Safety criteria - All cause death or SAE possibly related to cipargamin (as per sponsor)

**Lack of efficacy criteria – Use of IV artesunate as rescue medication (as per protocol defined criteria) in participants randomized to IV cipargamin

Number and percent of patient meeting with safety criteria and lack of efficacy criteria will be presented by cohort and treatment regimen as well in pooled cohorts 1-5.

3 Sample size calculation

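### The protocol does not settle whether IV artesunate after the third cipargamin dose, in a parasite-free participant unable to take oral medication at 72 h, is continuation or rescue, and the lack-of-efficacy count depends on the answer

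*Protocol*

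**What the plan says.** **Protocol, treatment rules**

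- Section 6.1.4 caps cipargamin at three doses and continues: "Participants requiring prolonged IV treatment will be switched to IV artesunate and treated according to local practice". It sets no parasite condition.
- Section 4.2 takes the same line. Total IV duration, "either IV cipargamin followed by IV artesunate or IV artesunate alone) will be defined by the medical condition of the participants", together with the artesunate prescribing information.
- Section 6.2.1 lists when a cipargamin participant may be rescued with IV artesunate. The 72 h criterion is "Participants not able to take oral antimalarial along with presence of parasites at 72 hour post treatment initiation". Clinical decline and safety concerns due to cipargamin are separate routes with no parasite condition.
- Table 6-4 (Section 6.1.2.1), from 72 h onwards, decides on whether oral medication is feasible, but ends "Otherwise continue IV artesunate or switch to IV artesunate therapy (for participants on IV cipargamin as per Section 6.2.1").
- Footnote 18 of Table 8-1, matched in Table 8-2, says: "If cipargamin participants require IV therapy beyond 3 doses, refer rescue medication criteria".
- Section 6.7.2 gives two exits after at most three cipargamin doses: oral Coartem or rescue medication.
- Sections 4.1.1 and 6.2.2 rule out additional antimalarials except as rescue. Table 6-5 lists artesunate monotherapy as prohibited in the cipargamin arms except as rescue.

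**Counting and analysis rules**

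- Protocol Table 3-1 and SAP Table 2-14 count, for lack of efficacy, "Use of IV artesunate as rescue medication (as per protocol defined criteria) in participants randomized to IV cipargamin".
- SAP 2.4.2 says that for a participant randomized to cipargamin but "receiving IV artesunate per investigator's discretion, the IV artesunate will be classified as rescue medication".
- The DMC output list (SAP Table 2-13) glosses the lack-of-efficacy criterion simply as use of rescue medication.
- SAP Table 2-4 makes IV rescue before a visit a clinical failure at that visit. SAP 2.7.2.4 censors time to oral therapy at first IV rescue.

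**The concern.** The participant in question has had all three cipargamin doses and at 72 h is parasite-free, not clinically declining, without a cipargamin safety concern, and unable to take oral medication. Section 6.1.4 moves this participant to IV artesunate. Table 6-4 and footnote 18 send the same decision to Section 6.2.1, where no criterion is met. Section 4.1.1 and Table 6-5 then make artesunate outside rescue a prohibited drug.

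Three things depend on whether the switch is called rescue:

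1. **Pause rule.** The count that triggers a recruitment pause could include participants whose parasites have cleared, or leave them out, depending on who classifies them.
2. **Clinical success after 48 h.** A rescue label makes the participant a failure at every later visit. An artesunate participant needing the same extra IV days simply continues assigned treatment.
3. **Time to oral therapy.** The cipargamin participant is censored at the switch, while the artesunate participant stays at risk until oral therapy starts. The asymmetry affects precisely the slow recoverers.

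**Working it through.** **Step 1. Apply each passage to the same participant** (parasite-free, stable, no safety concern, unable to take oral medication at 72 h, three doses given).

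| Source | Result |
|---|---|
| Protocol 6.1.4, 4.2 | Switch to IV artesunate; parasites not considered |
| Protocol 6.2.1 | No criterion met |
| Protocol Table 6-4, 72 h row | Switch, but as per 6.2.1 |
| Protocol Tables 8-1 and 8-2, footnote 18 | Go to the rescue criteria |
| Protocol Tables 8-1 and 8-2, footnote 20 | Continue IV treatment and re-evaluate every 24 h |
| Protocol 6.7.2 | Coartem or rescue medication |
| Protocol 4.1.1, 6.2.2, Table 6-5 | Artesunate only as rescue |
| Protocol Table 3-1, SAP Table 2-14 | Not counted, if no 6.2.1 criterion is met |
| SAP 2.4.2 | Rescue, if given at the investigator's discretion |
| SAP Table 2-13 | Counted, if classed as rescue use |

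No single reading satisfies all rows.

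**Step 2. Reproduce the plan's own figures for the thresholds.** For n participants, threshold r and true rate p, the exact binomial tail is P(X ≥ r) = 1 − Σ C(n,k) pᵏ(1−p)ⁿ⁻ᵏ, summed over k = 0 to r−1.

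| n | r | At higher rate | At lower rate | SAP 3.2 states |
|---|---|---|---|---|
| 6 | 2 | 0.767 at 40% | 0.114 at 10% | >75%, <20% |
| 14 | 2 | 0.802 at 20% | 0.153 at 5% | about 80%, <20% |
| 20 | 3 | 0.794 at 20% | 0.161 at 7% | about 80%, <20% |
| 38 | 6 | 0.800 at 20% | 0.175 at 10% | about 80%, <20% |
| 116 | 14 | 0.845 at 15% | 0.160 at 9% | >80%, <20% |

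All agree with the SAP.

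**Step 3. Illustrate the effect of the label.** The documents give no rate for the disputed group, so let q be its share of a cipargamin arm, with q assumed at 2, 5 and 10%. If every such switch is counted and there is no other rescue, the pause probability is P(X ≥ r) at p = q. For n = 14, r = 2, q = 2%: 1 − 0.98¹⁴ − 14 × 0.02 × 0.98¹³ = 1 − 0.7536 − 0.2153 = 0.031.

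| Threshold | q = 2% | q = 5% | q = 10% |
|---|---|---|---|
| 2 of 14 | 3% | 15% | 42% |
| 6 of 38 | <0.1% | 1% | 17% |
| 14 of 116 | about 0 | 0.2% | 27% |

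If they are not counted, they contribute nothing.

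**Step 4. Add undisputed rescue.** With an assumed 5% rate of rescue that meets Section 6.2.1, the pause probability at q = 0, 2, 5, 10% is 0.15, 0.26, 0.42, 0.64 (2 of 14); 0.01, 0.05, 0.18, 0.52 (6 of 38); and 0.002, 0.03, 0.27, 0.85 (14 of 116).

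**Step 5. Timing.** The decision falls at 72 h, after the 12 h primary and 48 h key secondary assessments, so neither can change.

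**The case against.** The strongest reply is that the treatment itself is not really in doubt. A reader might infer that this participant gets no antimalarial under Section 6.2.1. The documents do not support that. Section 6.2.1 is permissive, and no passage tells a site to stop IV treatment. Section 4.1 continues it until oral therapy is tolerated, and Sections 4.2, 6.1.2.1 and 6.7.2 and footnote 20 all point to further IV treatment or rescue. This stands, and it narrows the point to the status of the switch.

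It does not dispose of the point. Reading 6.1.4 as a separate non-rescue continuation fails because Table 6-4 and footnote 18 route the decision through 6.2.1, and Sections 4.1.1, 6.2.2 and Table 6-5 leave no non-rescue use of artesunate in this arm.

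A second reply is that Table 3-1 and SAP Table 2-14 define the pause count explicitly, while SAP 2.4.2 is a note on summarising medication. Taken alone, the explicit definition should govern. But the DMC output drops the qualifier, and neither SAP Table 2-4 nor SAP 2.7.2.4 limits rescue to the protocol criteria.

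Third, a miscount is recoverable. Reaching a threshold leads to a pause and DMC review, reviewers independent of the trial team see unblinded data (Protocol 6.4), and the SAP plans listings of parasite counts and severe-malaria signs over time for rescued patients. This stands for the pause rule. It does not help the clinical-success or censoring rules, which are applied by derivation.

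Fourth, the group may be small: SAP 5.8.4 expects most patients to be discharged by 72 h. That is fair, and is why 2% is shown. The same section says results after 24 h may be negative for all cipargamin patients. If so, those still unable to take oral medication at 72 h would mostly be parasite-free. That rests on oral drug in uncomplicated malaria, and Protocol 4.2 says the response in hyperparasitaemia remains to be established.

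**Conclusion.** The inconsistency is in current text and should be resolved, though it is narrow. It concerns one kind of cipargamin participant at 72 h and mainly whether the switch is continuation or rescue. Its consequences are for the lack-of-efficacy count, clinical success at visits after the switch, and censoring of time to oral therapy. Part of the clinical-success effect may be nominal at 72 h itself, since inability to drink counts as prostration and is already a failure. The rescue label matters more because it persists through Day 29.

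The size is unknown. The step 3 probabilities rest on assumed shares of 2 to 10%, independent participants and every switch being counted. They show that the label could matter most in the 14-participant cohort and little in the larger groups unless the share approaches 10%. It would be wrong to infer that a pause from parasite-free switches is likely, or that the study would stop because of them.

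**What to change.** 1. Reconcile Protocol 4.1.1, 6.1.2.1 (Table 6-4), 6.1.4, 6.2.1, 6.2.2, Table 6-5 and footnote 18 of Tables 8-1 and 8-2 with one another. Which clinical rule is right is for the sponsor and its clinical advisers; this review takes no position.
2. State in Protocol Table 3-1 and SAP Table 2-14 whether a switch to IV artesunate after the third cipargamin dose in a parasite-free participant counts toward lack of efficacy.
3. Record the reason for each IV artesunate use in the cipargamin arm.
4. Apply the same classification in SAP 2.4.2, SAP Table 2-4, SAP 2.7.2.4 and the rescue row of SAP Table 2-13.

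The cost is a wording amendment to the protocol, matching SAP text, and one reason field on the case report form. No extra participants are needed.

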6.2.2 Concomitant therapy

Prior medications are defined as drugs taken and stopped prior to the first dose of study medication. In this study, all medication administered or taken by the participants up to 72 hours prior first dose has to be reported as prior medication in the appropriate Case Report Forms.

Severe malaria is a multisystem disease and requires treatment for the various signs and symptoms that occur. These will be treated according to the local clinical practice but should not include the administration of additional antimalarials unless the participant meets the criteria for rescue medication. The following medications are recommended for commonly observed symptoms:

- Paracetamol < 3g/day (or equivalent pediatric dosage; 10 to 15 mg/kg orally every 4 to 6 hours) may be used however, exact doses and time should be recorded appropriately.
- Metopimazine for repeated vomiting (or if not available, any other antiemetic which is not known to prolong QT and/or cause torsade de pointes)
- Beta-lactam antibiotics would be preferred in case of a bacterial infection (with the exception of amoxicillin-clavulanic acid because of its potential hepatotoxicity). If needed clindamycin can be given. All other antibiotics, new-quinolones included, should be avoided where possible.
- Lorazepam and furosemide. Diazepam should be allowed only when the suggested alternative lorazepam would not be available.
- Supportive therapy (e.g. blood or glucose transfusion, refer Study Manual)

Each concomitant drug must be individually assessed against all exclusion criteria/prohibited medication. If in doubt, the investigator should contact the Novartis medical/ monitor before randomizing a participant or allowing a new medication to be started. If the participant is already enrolled, Novartis should be contacted to determine if the participant should continue participation in the study, if the time permits based on participant condition.

All medications, procedures, and significant non-drug therapies (including physical therapy and blood transfusions) administered after the participant was enrolled into the study must be recorded on the appropriate Case Report Forms.

